7.5 Other Statistical Analyses

Baseline characteristics (age, stage of disease, initial estradiol, etc.) will be compared between the two study arms using t-tests for continuous measures and chi-square contingency table analyses for categorical variables. To minimize the effects of multiple testing, no formal analyses of patients' patterns of response over time (baseline, 4 and 12 weeks) are planned. Data will be plotted for each patient; any apparent patterns will be noted for testing in subsequent trials.

7.6 Data and safety monitoring plan

One of the principle investigators will meet with a trial coordinator on a weekly basis to review AEs, complete reporting forms, and determine if AEs were treatment related, disease related or unknown. Adverse events and serious adverse events will be reported monthly in the UCSF Breast Cancer Site Committee. This committee consists of a minimum of three medical oncologists specializing in the care of breast cancer, a radiation oncologist, a statistician, a breast cancer surgeon and several basic scientists with expertise in cancer biology. During this meeting, an ongoing account of AEs and SAEs will be reviewed and any unexpected toxicities will be discussed. The group will then address whether the AEs, SAEs, or unexpected toxicities justify early closure of the study.

8. STUDY MANAGEMENT

8.1 Audits and inspections

Authorized representatives of AstraZeneca, a regulatory authority, an Independent Ethics Committee (IEC) or an Institutional Review Board (IRB) may visit the centre to perform audits or inspections, including source data verification. The purpose of an AstraZeneca audit or inspection is to systematically and independently examine all study-related activities and documents to determine whether these activities were conducted, and data were recorded, analyzed, and accurately reported according to the protocol, Good Clinical Practice (GCP), guidelines of the International Conference on Harmonization (ICH), and any applicable regulatory requirements. The investigator should contact AstraZeneca immediately if contacted by a regulatory agency about an inspection at his or her centre.

9. ETHICS

9.1 Ethics review

The final study protocol, including the final version of the Written Informed Consent Form, will be approved by the UCSF Committee on Human Research (CHR) prior to patient enrollment. The investigator must submit written approval to AstraZeneca before he or she can enroll any subject into the study.

The principal investigator is responsible for informing the CHR of any amendment to the protocol in accordance with local requirements. In addition, the CHR must approve all advertising used to recruit subjects for the study. The protocol must be re-approved by the CHR annually. Progress reports and notifications of serious unexpected adverse drug reactions will be provided to the CHR according to local regulations and guidelines. The principal investigator is also responsible for providing the CHR with reports of any serious adverse drug reactions from any other study conducted with the investigational product. AstraZeneca will provide this information to the principal investigator.

If modifications are made to the protocol or informed consent document according to local requirements, the new version has to be approved by AstraZeneca.

9.2 Ethical conduct of the study

The study will be performed in accordance with ethical principles that have their origin in the Declaration of Helsinki and are consistent with ICH/Good Clinical Practice, applicable regulatory requirements.

9.3 Written informed consent

It is the responsibility of the investigator to ensure that each patient reads, understands, and signs a document of informed consent before the subject can participate in the study. The contents and process of obtaining informed consent should be in accordance with all applicable regulatory requirements.

The subject's signed and dated informed consent(s) must be obtained before conducting any procedure specifically for the study. The subject will receive a copy of the signed and dated form, and the original will be retained in the site's study records. It is the responsibility of the investigator or his/her designee to inform the patient that participation in the study is entirely voluntary, and that consent regarding study participation may be withdrawn at any time without penalty or loss of benefits to which the subject is otherwise entitled.

If modifications are made to the protocol or informed consent according to local requirements, the new version will be approved by AstraZeneca.

9.4 Subject data protection

In accordance with the Health Information Portability and Accountability Act (HIPAA), the Written Informed Consent Form must include a subject authorization to release medical information to AstraZeneca and/or allow AstraZeneca, a regulatory authority, or Institutional Review Board access to subject's medical information that includes all hospital records relevant to the study, including subjects' medical history.

10. EMERGENCY PROCEDURES

10.1 Procedures in case of medical emergency

This protocol does not involve treatments or interventions that are likely to result in a medical emergency, the principal investigator is responsible for ensuring that procedures and expertise are available to handle medical emergencies during the study.

10.2 Procedures in case of pregnancy

All patients enrolled in this study will be confirmed to be post-menopausal prior to study entry, and therefore pregnancy will not be a possible event.

Appendix A.

CARES Sexual Interest Four-Item Subscale

How much does each item apply to you in the past 4 weeks?

(0 = not at all...to....4 = very much)

I do not feel sexually attractive.

I do not think my partner(s) finds me sexually attractive.

I am not interested in having sex.

I do not think my partner(s) is interested in having sex with me.

CARES Sexual Dysfunction Four-Item Subscale

How much does each item apply to you in the past 4 weeks?

(0 = not at all...to....4 = very much)

I find that frequency of sexual intercourse has decreased.

I have difficulty becoming sexually aroused.

I have difficulty getting lubricated.

I have difficulty reaching orgasm.

Sexual Satisfaction One Item Measure

Overall, how satisfactory to you is your sexual relationship with your partner?

1= Extremely unsatisfactory

2 = Moderately unsatisfactory

3 = Slightly unsatisfactory

4 = Slightly satisfactory

5 = Moderately satisfactory

6= Extremely satisfactory

Appendix B. Description of the 3-point vaginal epithelium score

A number of vaginal changes occur with loss of estrogen. There is loss of the normal vaginal rugae and the resultant thin epithelium often has visible blood vessels. Petechiae relates to visually apparent spontaneous hemorrhage of these blood vessels within the vaginal epithelium. Friability relates to thin dry vaginal tissues that bleed easily to the touch. The color changes from pinkish to a pale white. Loss of lubrication occurs and the epithelium appears dry. A number of studies evaluating vaginal atrophy have used 3 -5 point scales to assess vaginal health indices. These assessments are not typically validated but allow for objective measurements by a clinician. We have chosen a common 3 point scale to assess the degree of atrophy with numeric values of 0 for none, 1 for mild and 2 for moderate or severe changes. Composite scores at baseline will then be compared to those at study termination.

Descriptive Assessment of Vaginal Mucosa

Vaginal atrophy score				
Signs of atrophy	None*	Mild	Moderate	Severe
Rugae	Normal number and depth	Reduced rugae	Rare rugae	Smooth vagina
Pallor	Normal pink	Light pink	Very pale	White or deep red
Petechiae	None	Bleeds on scraping	Bleeds on contact	Clearly seen
Mucosal thinning (elasticity)	Normal	Decreased	None	Stenosis
Dryness	Normal lubrication	Slightly decreased	Minimal lubrication	Dry

* Normal subject.

[figure not shown]
References of studies that have used similar 3-5 point vaginal assessment scales.

Eisberg et al. Endometrial and Vaginal Effects of low-dose estradiol delivered by vaginal ring or vaginal tablet. Climacteric 2005;8:83-92

Parsons A et al. Effect of Raloxifene on the Response to Conjugated Estrogen Vaginal Cream or Nonhormonal Moisturizers in Postmenopausal Vaginal Atrophy. Obstetrics & Gynecology 2003;101:346-352

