3. STUDY PLAN AND PROCEDURES

3.1 Overall study design

This will be a single institution open label randomized Phase II study evaluating intravaginal testosterone cream vs. the Estring for vaginal dryness and/or decreased libido in early breast cancer patients treated with an aromatase inhibitor. Up to 80 early stage breast cancer patients will be enrolled over 36-48 months in order to have a total of 70 evaluable patients. To be considered evaluable, patients must complete their baseline evaluation and week 4 safety blood draw. Randomization of patients will attempt to balance the number of patients in each group based on self reported or medically documented depression, use of antidepressants, and relationship status (single vs. partnered). Patients will be randomized to a 12 week course of treatment with either:

- Testosterone Cream 1% micronized in velvachol - 0.5 gm of cream vaginally 3 times a week for total of 12 weeks of treatment
- Estring 2mg ring inserted vaginally once every 12 weeks

Patients will complete quality of life surveys including the CARES Sexual Interest and Sexual Dysfunction Subscales (Appendix A), which includes a single item sexual satisfaction measure previously tested by Ganz, at day 1 (baseline), week 4, and at the end of week 12 (the survey may be done either in the clinic, or at home and then mailed/faxed). Patients will undergo a gynecologic exam at baseline and at the end of week 12 (or sooner if they withdraw from the study or experience unexpected side effects). During this exam, the vaginal epithelium will be assessed using a 3-point scale evaluating color, petechiae, friability and dryness (Appendix B). Within each treatment group, composite scores of the vaginal epithelium at baseline will be compared to composite scores at study termination.

Serum estradiol assays sent to the UCSF clinical laboratory are sent out to Quest Diagnostics, which uses extraction chromatography RIA for their ultra-sensitive estradiol. Day 1 and week 4 samples will also be stored temporarily and then sent in batches to a specialized research lab which has developed an assay to quantify low levels of estradiol found in post-menopausal women. This assay is a radioimmunoassay after ether extraction, and has a sensitivity limit of 3pmol/l. Serum testosterone levels will also be sent to Quest, which uses an ultrasensitive testosterone measurement which is run by liquid chromatography tandem mass spectrometry.

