4.2 Testosterone cream 1% micronized in velvachol

There are a number of different esters of testosterone, including the commonly prescribed injectables of testosterone enanthate and testosterone cypionate, as well other esters such as acetate, propionate, phenylpropionate, isocaproate, caproate, decanoate, and undecanoate. Esterification of testosterone is done in order to improve the solubility of testosterone in oil,

which in turn slows the release of the testosterone from the site at which it enters the body. A number of formulations of androgen replacement have been tested in men, including injections, oral supplementation (either testosterone undecanoate, methyltestosterone, oxandrolone, or DHEA), transdermal testosterone patches, testosterone creams or gels, and subcutaneous testosterone implants. Based on a number of studies, the transdermal route (either patch, cream, or gel) appears to have the most favorable pharmacokinetic properties of available testosterone preparations tested in women.

TESTOSTERONE, MICRONIZED, USP (T1006)

Synonyms: 4-Androsten-17beta-ol-3-one; 17beta-Hydroxy-4-androsten-3-one
(C₁₉H₂₈O₂ : F.W. 288.42)

Testosterone cream will be produced by the UCSF Drug Product Services. The pharmacy has provided us with details of the preparation of the testosterone cream as follows:

The appropriate amount of pure testosterone chemical is weighed to produce a 1% concentration. The powder is levigated with mineral oil, and then this mixture is brought to the desired volume with velvachol.

Velvachol is a water-miscible compounding vehicle in a non-sticky, non-greasy, odorless base that is compatible with a wide variety of chemicals used in topical therapy. Velvachol is stable and neutral in reaction, and washes easily from the hair, skin and clothes. It is physically compatible with acids, bases, strong electrolytes and many other medications commonly applied to the skin. Velvachol is formulated in a hydro-philic emulsion-type base.

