4.3 Doses and treatment regimens

- Testosterone Cream 1% micronized in velvachol - 0.5 gm of cream vaginally 3 times a week for total of 12 weeks of treatment
- ESTRING 2mg ring inserted vaginally once every 12 weeks

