4.5 Pre-study, concomitant and post-study treatment(s)

Use of vaginal hormonal products (rings, inserts, creams, gels) containing estrogens or androgens within the past 90 days is not permitted.

Treatment with any type of oral, injectable or topical form of estrogen or androgen therapy including natural supplements marketed as hormone replacement products is not permitted during the 12 weeks of study treatment. Initiation or change in usage pattern of moisturizing agent, herbal or alternative medicine to manage the symptoms of vaginal dryness is not permitted during the 12 weeks of treatment.

There are no limitations on post-study treatments.

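### The epithelium composite grades visible lubrication, but the week-12 exam is not tied to the last cream application, so vehicle residue could be scored as improvement in the cream arm

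*Protocol*

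**What the plan says.** Section 3.1 plans a gynecologic exam at baseline and at the end of week 12, or sooner on withdrawal or unexpected side effects. At that exam "the vaginal epithelium will be assessed using a 3-point scale evaluating color, petechiae, friability and dryness". The planned analysis is: "Within each treatment group, composite scores of the vaginal epithelium at baseline will be compared to composite scores at study termination".

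Appendix B explains the grading. Of the atrophic vagina it says "Loss of lubrication occurs and the epithelium appears dry", and its dryness row is graded by the amount of lubrication present. Signs take "numeric values of 0 for none, 1 for mild and 2 for moderate or severe changes". It then repeats the planned comparison: "Composite scores at baseline will then be compared to those at study termination".

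The study plan in 3.2 places the week-12 visit on days 79-89, that is, day 84 plus or minus 5 days. Footnote d describes the scoring and gives no condition on recent product use.

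Section 4.3 gives the cream regimen as "0.5 gm of cream vaginally 3 times a week for total of 12 weeks of treatment". Section 4.2 describes how the cream is made: "The powder is levigated with mineral oil, and then this mixture is brought to the desired volume with velvachol". It describes velvachol as an emulsion-type base that mixes with water and washes off easily. Section 4.4 allows patients to go on using leftover cream after week 12.

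On other products, 4.5 states that "Initiation or change in usage pattern of moisturizing agent, herbal or alternative medicine to manage the symptoms of vaginal dryness is not permitted" during treatment. Exclusion criterion 3 in 3.3.3 lets earlier users of moisturizers continue in the same pattern.

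**The concern.** A dryness grade read from visible lubrication cannot by itself distinguish moisture produced by the tissue from a product left on its surface. At the termination exam a woman in the cream arm may have applied an oil-and-emulsion product hours or days before, and nothing in the protocol controls or records which. At baseline she has not yet used the study cream. The ring has no such vehicle.

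Any residue effect would therefore act in one direction, at one time point and in one arm. It would enter the planned baseline-to-termination comparison for the cream as apparent improvement. The protocol's own rules on moisturizers show that it regards topical products as relevant to vaginal dryness. The trial is open label, no masked assessor is described, and this composite is the only clinician-graded measure of atrophy in the schedule. If time since last use is not recorded, the artefact cannot be examined afterwards.

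**Working it through.** The protocol gives no sample size, SD, power or named test for this score, so there is no stated figure to reproduce. The check has three parts.

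**1. Is there any separation between application and exam?** Setting the sections side by side:
- 3.1 and 3.2 fix the exam by study day only.
- 3.3.5 brings the week-12 procedures forward on early discontinuation, again with no reference to last use.
- 4.3 runs cream use through week 12, and 4.4 permits use beyond it, so a late-window exam is not necessarily off cream.
- Appendix B and footnote d of 3.2 set no interval and no recording of last use.

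There is no separation. Average spacing is 7 × 24 / 3 = 56 hours. With applications on three separate days, 3 of 7 days (43%) are application days and 4 of 7 are not.

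**2. How much of the score is exposed?** Each sign scores at most 2. If the signs are summed:
- four signs in 3.1: maximum 4 × 2 = 8, dryness share 2/8 = 25%;
- five rows in the Appendix B table: maximum 5 × 2 = 10, dryness share 2/10 = 20%.

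**3. What could residue do to the within-arm comparison?** This is an illustration only.

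Inputs:
- n = 35 evaluable per arm (7.3).
- Assumed: no true tissue change; dryness 1 point lower in a share f of cream patients; SD of the composite change between 1 and 3; a two-sided 5% paired t-test.

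Formulas: mean shift = f × 1; d = f / SD; noncentrality = d × √35. The probability of significance is P(|T| > t(0.975; 34 df)), where T is noncentral t with 34 df.

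Example: f = 0.50 and SD = 2 give d = 0.25, noncentrality 0.25 × 5.92 = 1.48, probability 30%.

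| Share affected | Mean shift | SD 1 | SD 1.5 | SD 2 | SD 3 |
|---|---|---|---|---|---|
| 10% | 0.10 | 9% | 7% | 6% | 5% |
| 25% | 0.25 | 30% | 16% | 11% | 8% |
| 50% | 0.50 | 82% | 48% | 30% | 16% |

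With no shift the figure is 5% by construction. The top-right cell (5.4% before rounding) is therefore practically no effect, and the bottom-left cell is a serious one.

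**The case against.** The strongest objection is that residue at the exam is conjecture. The dose is 0.5 g, applications are on average 56 hours apart, and 4.2 describes a base that is not greasy and washes off easily. This stands: the documents do not show that residue persists, so no particular size can be claimed. They do not exclude it either, least of all for an exam on the day of an application.

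Several features would also dampen a shift. Moderate and severe changes both score 2, so a move between them changes nothing. Women may enter for decreased libido alone, and those with dryness graded 0 at baseline cannot improve. Continuing moisturizer users may have product present at baseline too. These points stand and are reasons to show small shares affected as well as large ones.

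A reader might infer that a cream-versus-ring contrast of the score is biased. The protocol plans no such contrast: 3.1 compares within each arm, and the between-arm outcome comparison in 7.3 concerns CARES. The point would matter there only if someone later made that comparison.

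A reader might also infer that the trial's conclusions are at risk. They are not. The score is absent from the objectives in section 2 and from section 7, and no stopping or safety rule uses it.

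Finally, it can be said that this is an omission suited to an exam form, and that an analysis without dryness could sit in a statistical analysis plan. That is fair for the extra analysis. Exam timing and the recording of last use, however, have to be settled before the exam takes place.

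**Conclusion.** The point holds as a minor design weakness. A planned within-arm comparison includes a sign that the cream's vehicle could alter directly, and the protocol neither limits nor records the exposure. Under the stated assumptions (1-point shift in 10-50% of cream patients, SD of change 1-3, n = 35, paired t-test), the probability of a significant change without any tissue effect runs from about 5% to 82%. Neither the share affected, the SD nor the test comes from the documents, so the range shows what is possible and does not estimate what will happen.

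It would go too far to conclude that improvement seen with the cream must be spurious. That would require persistent residue in most women, which the documents do not support. The estradiol endpoint, the two-stage rule and the CARES analyses are unaffected.

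**What to change.** In Appendix B and footnote d of 3.2:
- Schedule the termination scoring before any application that day, and on a non-application day where possible within the existing window. Dosing and the permitted moisturizer pattern stay as they are.
- Record time since last use of cream or moisturizer at both scored exams.
- Report the composite with and without the dryness sign.

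A stricter rule, such as no cream or moisturizer on the exam day or the day before, is not advisable. It could conflict with the fixed moisturizer pattern in 3.3.3 and 4.5. With alternate-day applications it would also rule out 3 + 3 = 6 of 7 days, leaving about one eligible day a week.

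While editing, reconcile the four signs named in 3.1 and 3.2 with the five rows of the Appendix B table, since this decides the weight of dryness in the composite.

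The cost is slightly tighter scheduling of the week-12 exam, one form field and one extra analysis.

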Appendix C.

APPENDIX D.: Blood Specimen Collection and Handling Instructions for Research serum estradiol assay

At baseline and Week 4, one sample will be collected for standard hormone testing at UCSF or Quest Diagnostic® labs (routine lab test), and a second sample will be collected for a specialized low-level estradiol assay (research lab test).

- The lab slip should specify that an extra sample of blood is to be collected for the study.
- At least 3-4 ml of blood is needed to create the research serum sample that will be sent for low-level estradiol assay.
- The study personnel responsible for obtaining the research sample from the lab should label the red top vacutainer tube with the patient's identification (patient number and patient initials), protocol number (067519), date and time of blood draw (dd-MMM-yyyy format for the date (i.e. 01-JAN-2003) and 24:00 hour clock format for the time).
- The **research lab sample** will be collected by the lab technician in a red top vacutainer at the time the standard hormone blood sample is collected using standard venipuncture techniques.

Serum Collection Tube:

1. 4-6 mL red top vacutainer tube

Specimen Transfer Tube:

1. Non-sterile polypropylene specimen tube (cryovial) with screw cap.
2. Freezer resistant specimen label to fit the cryovial.

Serum Collection and Shipping Instructions

1. Draw 3-4 mL of blood (yielding ≥ 0.5 mL of serum) into a red top vacutainer tube at each designated specimen timepoint using standard venipuncture techniques.
2. After collection, the study personnel will take the sample to the centrifuge.
3. Allow the blood to clot upright at room temperature for 30 minutes.
4. Centrifuge the sample for approximately 15 minutes.
5. Completely fill out the label with the corresponding patient's identification (patient ID number and patient initials), protocol number (067519), date and time of blood draw (dd-MMM-yyyy format for the date (i.e. 01-JAN-2003) and 24:00 hour clock format for the time) and affix it to one of the room temperature polypropylene specimen tubes.
 - A freezer resistant label should be used so that water or freezing temperatures do not destroy the label since samples must remain frozen until shipment

6. Draw off the supernatant and pipette 0.5mL – 1.5 mL of the serum into the properly labeled polypropylene specimen tube.
7. Freeze the samples at or below -80°C until ready for shipment. The freezer location is: Tissue Core freezer #5441 in room N155 located at [name], first floor.

Shipping Serum Samples

1. Research personnel will follow the “*UCSF Guide to Shipping with Dry Ice*” to package and ship the samples internationally using dry ice. Instructions are found on the UCSF Office of Environmental Health and Safety website:
<http://www.ehs.ucsf.edu/Manuals/SDIM/SDIM.pdf>

An inventory list all of the samples being sent must be included in each shipment. A copy of the shipping list should remain at the site. Prior to shipment, send email to [name] at [contact] alerting her to the impending shipment of the samples, and attach an electronic copy of the inventory list of samples being sent.

2. To prevent damage to the frozen samples, care should be taken to ship the samples on a Monday, or Tuesday AND avoid shipping one or two days prior to a public holiday either at the country of origin or the country of destination.

3. The shipping address is:

[name]
The Academic Department of Biochemistry
The Royal Marsden NHS Trust
[name]
London
[name]
UK
